6.3 Other Study Related Definitions

Analytical Study Week Assignments

Analytical windows will be used to assign parameter measurements to study weeks.

The algorithm is provided in [Appendix A](#).

Actual Treatment Group

A subject's actual treatment group in the parent study is the randomized treatment group, unless the subject receives treatment throughout the parent study that is different than the randomized treatment group assignment, in which case the actual treatment group is the treatment received.

Investigational Product (IP)

IP is AMG 145 SC 420 mg QM

IP Exposure Period in Months

IP Exposure Period = [min (Last IP Dose Date + 28 days, EOS Date) - First IP Dose Date +1] / 365.25 * 12

Study Exposure Period in Months

For each randomized subject, Study Exposure Period = (EOS date – Enrollment Date + 1) / 365.25 * 12

Treatment Emergent Adverse Event (TEAE)

Treatment emergent adverse events are adverse events occurring between the first dose of IP and EOS. Treatment emergent adverse events can be identified if answer to the AE eCRF question “Did event start before first dose of investigational product?” is No or missing.

Reflexive Approach for LDL-C and VLDL-C

For all analyses related to LDL-C and VLDL-C, unless specified otherwise, a reflexive approach will be used. When calculated LDL-C is less than 40 mg/dL or triglycerides are > 400 mg/dL, the UC LDL-C and VLDL-C value from the same blood sample will be used instead of calculated LDL-C and VLDL-C, if available.

7. Analysis Subsets

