5. SUBJECT ENROLLMENT

Before subjects may be entered into the study, Amgen requires a copy of the site's written independent ethics committee and/or institutional review board (IEC/IRB) approval of the protocol, informed consent form (ICF), and all other subject information and/or recruitment material, if applicable (see [Section 11.2](#)). All subjects must personally sign and date the informed consent form before commencement of study specific procedures. A subject is considered enrolled once they have completed their end of study visit in the parent protocol and signed the informed consent form.

All subjects who enter the study will keep the same subject identification number from the parent study.

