7. STUDY PROCEDURES

Subjects that successfully complete study 20120153 and completed IP (evolocumab) in study 20120153 will be eligible to enroll in this study. In addition, subjects will need to meet eligibility criteria. Subjects will need to sign a new study informed consent form. Subject numbers will be the same as those in their parent study. Subjects will visit the site on Day 1 and week 4. Thereafter, subjects will visit the site quarterly for the first year and two additional times during year 2. During these visits vital signs will be obtained and adverse events (AEs), serious adverse events (SAEs), concomitant medications will be recorded, and central laboratory tests will be performed. All subjects will receive open-label evolocumab for approximately 2 years (or until the investigator's recommendation of discontinuation, Amgen's recommendation of discontinuation, the subject's decision to discontinue for any reason, or until an administrative decision is

made to close the study). For the purpose of this study, a month is defined as 4 weeks and a quarter is defined as 12 weeks.

Written informed consent must be obtained and will be implemented before protocol specific procedures are carried out. The risks and benefits of participating in the study will be verbally explained to each potential subject prior to entering into the study. The procedures to be performed at each clinic visit are described below. IP should not be administered until all study procedures are completed at each visit. Subject visit schedule will be the same for all subjects. **In addition to the protocol-specified study procedures and assessments described below, investigators should continue to routinely monitor subjects according to local disease management guidelines and perform assessments (eg. ECG, hemoglobin A1c, eGFR, and hematology), as applicable, in routine care.**

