7.1 Schedule of Assessments

Study Day / Timepoint	YEAR 1				YEAR 2	
	EOS Parent Day 1 OLE ^a	Week 4	Quarterly Visits Weeks: 12, 24, 36, and 48	Week 52	Month 6 (Week 76)	Year 2 (Wk 104) EOS/ET OLE ^e
General Procedures						
Medical History	X					
Informed consent	X					
Vital Signs (HR, BP)	X	X	X	X	X	X
AEs/SAEs/CV Events	X	X	X	X	X	X
Concomitant medication	X	X	X	X	X	X
Body Weight	X			X		X
Waist circumference	X			X		X
Physical exam	X			X		X
Central Laboratory						
Fasting Lipids	X	X	X	X	X	X
Chemistry	X	X	X	X	X	X
Serum pregnancy (females of childbearing potential) and FSH	X ^b	X ^c	X ^c	X ^c	X ^c	X
Investigational Product						
IP dispense ^d	X	X	X	X	X	
IP reconcile	X	X	X	X	X	X

^a D1 = day of first administration of investigational product for the open-label extension (OLE); subjects will sign a new OLE consent.

^b FSH = in applicable subjects for study entry only – see [exclusion criteria](#)

^c Serum pregnancy testing will occur at week 4, week 24, week 52, and every 6 months thereafter.

^d Subjects or caregivers will administer evolocumab monthly both at site visits and between site visits. Last IP will be administered at week 100.

^e The EOS procedures should be used as a guide for the depth of information obtained for any subject that elects to discontinue IP but continue via follow-up (see [section 8](#)).

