7.1 Full Analysis Set

The Full Analysis Set (FAS) includes all subjects enrolled in this study. This analysis set will be used for all final analyses.

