7.2 Interim Analyses Set

The Interim Analysis Set (IAS) includes all subjects from the FAS that complete the Week 52 visit at the time of interim analysis, or discontinued study prior to Week 52.

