10.6 Safety Analyses

10.6.1 Analyses of Primary Endpoints

Adverse events will be coded using the latest version of Medical Dictionary for Regulatory Activities (MedDRA). Severity of AEs will be graded using the CTCAE ([Appendix B](#)) and recorded on the eCRF. All adverse event tables will be summarized by actual treatment group in Study 20120153.

Subject incidence of all TEAEs, serious TEAEs, and TEAEs leading to withdrawal of investigational product will be tabulated by system organ class, high level term and preferred term in descending order of frequency.

Subject incidence of device-related TEAEs will be tabulated by high level group term (including “administrative site reactions” and “device issues”) and preferred term in descending order of frequency.

Summaries of all TEAEs and serious TEAEs occurring in at least 1% of the subjects by preferred term in any treatment group will be provided in descending order of frequency.

Subject incidence of treatment emergent events of interest (EOIs) will be summarized according to the EOI search strategy categories defined by the EOI steering committee. The definition of each EOI may be modified and new EOI may be added based on findings from ongoing pharmacovigilance. Updates of the search strategy due to MedDRA upgrades or other reasons may not trigger a SAP amendment. However, the most recent EOIs per Amgen EOI search strategy will be used at the time of the analysis and these search terms will be included in an appendix of the study report. As of the date of preparing this version, the current EOI are:

- potential hypersensitivity events (based on narrow and broad search strategies)
- potential injection site reaction events (based on narrow and broad search strategies)
- potential muscle events (based on narrow and broad search strategies)
- potential neurocognitive events (based on high level group terms)
- potential hepatitis C infection (based on narrow and broad search strategies)
- transaminase elevations and potential hepatic disorders (based on narrow and broad search strategies)

Overall AE summary will be also be provided in subgroups specified in [Section 7.3](#).

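### The treatment-emergent AE tables count every enrolled subject, dosed or not, and the eCRF-flag sentence in SAP 6.3 does not repeat the limits of the definition it serves (minor)

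*SAP*

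**What the plan says.** SAP 6.3 gives the definition, "Treatment emergent adverse events are adverse events occurring between the first dose of IP and EOS", and then an operational route: "Treatment emergent adverse events can be identified if answer to the AE eCRF question" on onset before first dose is No or missing. That second sentence mentions neither EOS nor a dose on record.

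SAP 10.6.1 builds the primary-endpoint tables on this: "Subject incidence of all TEAEs, serious TEAEs, and TEAEs leading to withdrawal of investigational product will be tabulated". It groups subjects by actual parent-study treatment and names no analysis set, so SAP 7.1 governs: "The Full Analysis Set (FAS) includes all subjects enrolled in this study. This analysis set will be used for all final analyses". The only other set, in SAP 7.2, is drawn from it and "includes all subjects from the FAS that complete the Week 52 visit at the time of interim analysis, or discontinued study prior to Week 52".

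Enrolment is defined in Protocol 5: "A subject is considered enrolled once they have completed their end of study visit in the parent protocol and signed the informed consent form". SAP 6.1 dates enrolment at the consent signature. Neither requires a dose. Protocol 7.2.1 intends the parent week 80 visit and extension Day 1 to fall on the same day, but its heading allows 14 further days.

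Protocol 9.1.2 collects AEs from consent to EOS. Protocol 9.2.2 collects serious events to EOS or 30 days after the last dose, whichever is later.

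**The concern.** The primary endpoint is the subject incidence of adverse events. Two features of the SAP loosen that figure.

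The first is the denominator. It is set at consent, whereas the numerator opens at first dose. An enrolled subject who is never dosed can only dilute the percentage, and in a safety study a diluted percentage looks favourable. Other SAP quantities also have no value for such a subject: study day (SAP 6.1), IP exposure period (SAP 6.3) and the Study Day 1 defaults for partial dates (SAP 9.3.2, Table 1) all need a first dose date.

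The second is the numerator. A programmer who codes only the flag sentence would count a serious event with onset after EOS, and a missing-flag event in an undosed subject or before dosing. A programmer who codes the definition would not. The same paragraph could then yield two different counts.

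**Working it through.** **Planned size.** Protocol 10.2 and SAP 3.2: 950 × 0.75 × 0.9 = 641.25, rounded up to 642. The plan's figure reproduces, and 642 is used as the expected full-analysis-set denominator.

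**Denominator.** Let p be the incidence among dosed subjects and k the number enrolled but undosed. The tables would report p × (642 − k)/642, a shortfall of p × k/642. The documents give neither p nor k, so both are assumptions.

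| Undosed k | Reported at p = 80% | Shortfall, p = 80% | Shortfall, p = 50% | Shortfall, p = 10% |
|---|---|---|---|---|
| 0 | 80.0% | 0 | 0 | 0 |
| 1 | 79.9% | 0.12 points | 0.08 | 0.02 |
| 3 | 79.6% | 0.37 | 0.23 | 0.05 |
| 6 | 79.25% | 0.75 | 0.47 | 0.09 |

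Within one parent-treatment group the formula is the same, with that group's own k and size. For a shortfall of about 4 points, 5% of subjects (32) would have to be undosed at p = 80%: 0.80 × 32/642 = 3.99 points. Nothing in the documents suggests such a number.

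**Serious events after EOS, completers.**
- Last dose at week 100 (Protocol 7.1, footnote d): 7 × 100 + 1 = day 701. Collection runs to 701 + 30 = day 731.
- EOS at week 104: 7 × 104 + 1 = day 729. Nominal gap: 731 − 729 = 2 days.
- With ±7 days on the last dose (a) and on EOS (b), the gap is max(0, 2 + a − b), which ranges from 0 to 16 days. If all 15 × 15 = 225 combinations are equally likely (an assumption), the mean is 814/225 = 3.62 days, and 91/225 = 40.4% have no gap.

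Assume 10 to 20 serious events per 100 person-years in all 642 subjects. Under a Poisson model, the share with no earlier serious event over two years is exp(−0.2) = 0.819 to exp(−0.4) = 0.670.

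| Gap | Person-years | Serious events | Subjects newly counted | Points of 642 |
|---|---|---|---|---|
| 2 days | 642 × 2/365.25 = 3.52 | 0.35–0.70 | 0.29–0.47 | 0.04–0.07 |
| 3.62 days | 642 × 3.62/365.25 = 6.36 | 0.64–1.27 | 0.52–0.85 | 0.08–0.13 |

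**Serious events after EOS, early terminators.** The gap reaches 30 days if EOS falls on the day of the last dose. If an assumed 5–10% of subjects (32.1–64.2) all had the full gap, that is 2.64–5.27 person-years, or 0.26–1.05 serious events. Given that assumed fraction, this is an upper bound: Protocol 8.1 asks subjects who stop IP to stay under observation, and there is no gap once EOS is more than 30 days after the last dose.

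Each subject wrongly counted adds 1/642 = 0.16 points. Non-serious events are unaffected at the EOS end, because their collection stops at EOS.

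**The case against.** The strongest reply is that almost nothing is at stake. The sentence before the flag rule states both limits, EOS is a defined date (SAP 6.1), and the flag asks only about onset before first dose. It can reasonably be read as implementing the lower limit and nothing else. Treating a missing answer as treatment-emergent is a deliberate conservative choice, consistent with the partial-date defaults in SAP Table 1. All of this stands. The flag issue is one of consistency; the SAP does not contain two rival definitions.

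A reader might also infer that entry testing routinely creates undosed subjects. Protocol 7 says "Written informed consent must be obtained and will be implemented before protocol specific procedures are carried out", and footnote b of Protocol 7.1 says "FSH = in applicable subjects for study entry only", so entry samples follow consent. The documents do not carry that inference far. Protocol 7.2.1 describes subjects who already meet the criteria as the ones who sign consent. It holds the first injection until blood is drawn, not until results return, and the samples go to a central laboratory. On a same-day schedule, an adverse result would probably arrive after dosing. What remains is a subject who withdraws, or whose result arrives, within the 14-day allowance. That may be nobody.

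Finally, Protocol 10.1.5 applies the full analysis set to all analyses without exception, and only the synopsis leaves room for one. So a dosed-subject set cannot be called fully consistent with the protocol. That point stands and shapes the fix.

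**Conclusion.** The point holds as a minor correction. Under the stated rules, any enrolled but undosed subject lowers the reported incidence, by about 0.1 point each at an assumed 80% and N = 642, and by nothing if there are none. The flag sentence, taken alone, omits the EOS limit and the dose requirement. For completers, the consequence is fewer than one additional subject under the assumed serious-event rates.

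A reader might infer that the primary safety result is materially biased in the sponsor's favour. The documents do not support that. They give no count of undosed subjects, same-day dosing is intended, and the two effects pull in opposite directions: the denominator lowers incidence, while a literal flag rule raises it. No net direction is claimed. The analyses are descriptive, so no inference is affected. The incidence, undosed count, serious-event rate, uniform use of windows and early-termination fraction are all assumptions. The textual gap does not depend on them; only its size does.

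**What to change.** 1. **SAP 7.** Define a Safety Analysis Set: full-analysis-set subjects with at least one extension dose of evolocumab. Use it as the denominator for the AE, event-of-interest and exposure tables, and use its intersection with the interim set at one year. Keep the existing sets for disposition, and report the number enrolled but not dosed. Record this as a departure from Protocol 10.1.5, relying on the synopsis wording that permits exceptions.

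2. **SAP 6.3.** State that the flag implements only the lower limit, and that a treatment-emergent event also requires a recorded first extension dose and onset on or before EOS. Where the flag is missing, use the onset date if it is usable, with the Table 1 defaults for partial dates. Otherwise keep the present conservative rule and count the event in dosed subjects, so that an event with neither flag nor date still has a classification.

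3. **Optional.** List serious events with onset after EOS and within 30 days of the last dose. This is a matter of presentation.

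The cost is one population flag and a few sentences of SAP text, plus the listing if wanted. The only downside is a possibly slightly less favourable incidence.

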8. REMOVAL AND REPLACEMENT OF SUBJECTS

8.1 Removal of Subjects

Subjects have the right to withdraw from the treatment, procedures, or study at any time and for any reason without prejudice to their future medical care by the physician or at the institution.

Withdrawal of full consent for a study means that the subject does not wish to receive further protocol-required therapies or procedures, and the subject does not wish to or is unable to continue further study participation including any follow-up in person, by phone, through 3rd parties including relatives or friends, via discussion with other treating physicians, and by use of medical records; subject data up to withdrawal of full consent will be included in the analysis of the study. Any subject may withdraw full consent to participate in the study at any time during the study. The investigator will discuss with the subject appropriate procedures for withdrawal from the study. The investigator should ask the subject's consent to perform the procedures listed under the final study visit.

Subjects may decline to continue receiving IP or other protocol-required procedures at any time during the study. If this occurs, the investigator will discuss with the subject appropriate procedures for discontinuation from IP or other protocol-required procedures and should encourage the subject to continue with collection of data, including endpoints and adverse events. These subjects, as well as those who have stopped receiving IP or other protocol-required procedures for other reasons (eg, investigator or sponsor concern) should continue the schedule of study observations. If the subject is unable or unwilling to continue the schedule of observation, the investigators should clarify what type of follow-up the subject is agreeable to: in person, by phone/mail, through family/friends, in correspondence/communication with other physicians, and/or from review of the medical records. For these subjects, the EOS procedures should be used as a guide for the depth of information obtained for any subject that elects to continue via follow-up.

Should a subject (or a legally acceptable representative) request or decide to withdraw from the study, all efforts will be made to complete and report the observations as thoroughly as possible up to the date of withdrawal. All information should be reported on the applicable eCRFs.

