2.1 Primary

To characterize the safety and tolerability of long-term administration of evolocumab in subjects with known coronary artery disease and hypercholesterolemia.

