10.6.2 Analyses of Exploratory Endpoints

Death, myocardial infarction, hospitalization for unstable angina, coronary revascularization, stroke, TIA, and hospitalization for heart failure will be adjudicated by an independent CEC. Non-coronary revascularizations will be collected on the eCRF and will not be adjudicated. Subject incidence of clinical events will be summarized by actual treatment group in Study 20120153.

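### Treatment-emergent events run to end of study with no last-dose limit, and no planned table shows the events that occur while evolocumab is being given

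*SAP*

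**What the plan says.** - **Event window.** SAP 6.3: "Treatment emergent adverse events are adverse events occurring between the first dose of IP and EOS". The rule that applies it uses one eCRF question, "Did event start before first dose of investigational product", with No or missing counted as treatment-emergent. Neither part refers to the last dose. Protocol 10.4.2.1 uses the term without defining it, so SAP 6.3 is the only definition.
- **Follow-up after stopping IP.** Protocol 8.1 says that subjects who have stopped "should continue the schedule of study observations", and that for those who decline IP the investigator "should encourage the subject to continue with collection of data, including endpoints and adverse events". Protocol 9.1.2 collects adverse events from consent to EOS, whether or not the subject is on drug. Footnote e of the schedule in Protocol 7.1 also foresees subjects who stop IP and remain in follow-up.
- **On-drug period.** SAP 6.3 already has one: the IP Exposure Period ends at "min (Last IP Dose Date + 28 days, EOS Date").
- **Objective.** SAP 2.1: "To characterize the safety and tolerability of long-term administration of evolocumab".
- **Planned tables.** SAP 10.6.1 tabulates subject incidence of all treatment-emergent events, serious ones, those leading to IP withdrawal, device-related ones, those in at least 1% of subjects, events of interest, and an overall summary by subgroup. For the adjudicated events, SAP 10.6.2 says: "Subject incidence of clinical events will be summarized by actual treatment group in Study 20120153". None of these tables has a window tied to the last dose.

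**The concern.** The primary objective concerns the safety of giving the drug over a long period. A subject who stops early but stays in the study goes on adding events to the primary tables for as long as follow-up lasts. In a high-risk coronary population, background events will occur in that time. The same holds for the adjudicated events, whose stated purpose (SAP 2.3) is to describe event rates in subjects treated with evolocumab.

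A reader of the planned outputs could not tell which events arose on drug. The exposure table in SAP 10.6.5 would describe time on drug and the event tables would describe time in the study, with nothing to connect the two. If stopping differed between the two parent-study groups, which the documents do not tell us, the off-drug share would also differ between table columns.

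**Working it through.** **The plan's own figure.** Protocol 10.2: 950 × 0.75 × 0.9 = 641.25, rounded up to 642. This reproduces. The event definition carries no figure of its own.

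**Inputs from the documents.** EOS target is study day 729 (Week 104, SAP Appendix A). The last planned dose is at Week 100 (Protocol 7.1, footnote d). A dose at week w falls on day 7w + 1. The on-drug period ends 28 days after the last dose (SAP 6.3).

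**Inputs assumed.** The share stopping IP early is not in the documents; 5%, 10% and 20% are used. Last doses of stoppers are spread evenly over Weeks 0, 4, …, 96 (25 values). All stoppers stay to Week 104. The event rate is constant and unrelated to drug.

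**Step 1: off-drug days for one subject** = 729 − (last dose day + 28), not below zero.

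| Last dose | Off-drug days | Years |
|---|---|---|
| Day 1 | 729 − 29 = 700 | 1.92 |
| Week 12 | 729 − 113 = 616 | 1.69 |
| Week 24 | 729 − 197 = 532 | 1.46 |
| Week 52 | 729 − 393 = 336 | 0.92 |
| Week 76 | 729 − 561 = 168 | 0.46 |
| Week 100 (completer) | 729 − 729 = 0 | 0 |

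The subject dosed once has 29 / 365.25 × 12 = 0.95 months of IP exposure, and 700 / 729 = 96% of the event window is off drug. With a 30-day tail the maximum is 698 days (1.91 years); with a 15-week tail it is 623 days (1.71 years). At the one-year interim (cutoff day 365) it is 365 − 29 = 336 days.

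**Step 2: off-drug share of follow-up.** Mean off-drug time per stopper is 364 days, or 0.997 years. Total follow-up is 642 × 729 / 365.25 = 1,281 person-years.

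| Stopping share p | Off-drug person-years (642 × p × 0.997) | Share of 1,281 |
|---|---|---|
| 5% | 32 | 2.5% |
| 10% | 64 | 5.0% |
| 20% | 128 | 10.0% |

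**Step 3: effect on a tabulated incidence**, at an assumed 0.10 per year.
- To EOS, every subject: 1 − exp(−0.10 × 729 / 365.25) = 18.09%.
- On drug, stoppers only, averaged over the 25 last-dose weeks: 9.37%.
- On drug, whole table: (1 − p) × 18.09% + p × 9.37%.

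| p | To EOS | On drug | Difference (points) | Subjects of 642 |
|---|---|---|---|---|
| 5% | 18.1% | 17.7% | 0.44 | 2.8, about 3 |
| 10% | 18.1% | 17.2% | 0.87 | 5.6, about 6 |
| 20% | 18.1% | 16.3% | 1.74 | 11.2, about 11 |

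At 0.02 per year the differences are 0.6, 1.2 and 2.5 subjects. At 0.5 per year they are 8.4, 16.8 and 33.6.

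**The case against.** The strongest reply is that the window is deliberate. It matches the period over which the protocol collects adverse events, it is a whole-study summary that follows everyone regardless of stopping, and the study plans no inference. Because the statistic is crude subject incidence, off-drug follow-up can only add subjects with events; it cannot hide harm. All of this stands, and it is why the to-EOS tables should be kept.

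Some stronger readings are tempting, and the documents do not support them.
- A reader might infer a numerator and denominator error, because the SAP ends IP exposure 28 days after the last dose. No planned rate divides events by IP exposure, and SAP 6.3 also defines a Study Exposure Period running to EOS. The gap is between tables and not inside a statistic.
- A reader might quote 18% against 9%. That contrast applies only to stoppers, whom no planned table isolates. In the tabulated population the gap is under 2 points in the cases worked at 0.10 per year.
- A reader might take almost two years of off-drug time as typical. It is the maximum for one subject dosed once and followed to Week 104.
- A reader might take 30 days after the last dose as the protocol's limit for serious events. Protocol 9.2.2 sets the later of that date and EOS, so for an early stopper who stays in the study the limit is EOS.

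The follow-up assumption is also at the upper end. Protocol 8.1 allows withdrawal of full consent and reduced forms of contact, and entrants had already completed IP in the parent study (exclusion 4). Other outputs give some context: events leading to IP withdrawal, discontinuation by reason, and exposure. None of them separates on-drug from off-drug events.

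**Conclusion.** The point holds as a gap in the planned outputs. The to-EOS tables are valid for what they describe, but no table describes events during administration, although that is the primary objective and the SAP already defines the period needed.

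The likely effect on whole-table incidences is small: about 3, 6 or 11 subjects of 642 at an assumed 0.10 per year with 5%, 10% or 20% stopping. It is larger for commoner events and smaller for rarer ones. These figures rest on assumed stopping shares, uniform stopping times, complete follow-up of stoppers to Week 104 and a constant rate unrelated to drug. With less follow-up of stoppers the effect shrinks; with earlier stopping it grows. The change is worth making because it is cheap, and it does not imply that the existing tables are wrong.

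**What to change.** 1. In SAP 6.3, add an on-treatment flag for adverse events that start between the first dose in the extension and the earlier of last IP dose + 28 days and EOS. This is the SAP's own IP Exposure Period, so events and exposure then cover the same time. Keep the existing treatment-emergent definition.
2. In the same place, state how partial onset dates are treated at the end of the window. SAP 9.3.2, Table 1 generally moves them to the first of the month, 1 January or Study Day 1, which can pull an off-drug event into the on-treatment set.
3. In SAP 10.6.1 and 10.6.2, show all treatment-emergent events, serious ones, events of interest and adjudicated events for this window beside the to-EOS results.

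The dates needed, adverse event onset and last IP dose, are already collected, although the final home dose date is reported by the subject. Trial conduct does not change. The cost is SAP wording, a derived flag with its date rule, and one more set of tables with somewhat fewer events in the on-treatment set.
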